- [complementary and alternative medicine products](#) such as dietary supplements, substances generally recognized as safe (GRAS) when used to diagnose, cure mitigate, treat or prevent disease, or clinical studies of [e-cigarettes](#) examining a potential therapeutic purpose.

Does this protocol involve a drug including an FDA approved drug; unapproved use of an FDA approved drug; and/or an investigational drug?

 Yes NoIf yes, complete the questions below. Additional [study drug guidance](#).

LIST EACH DRUG INVOLVED IN STUDY IN THE SPACE BELOW

Drug Name:

Marijuana, alcohol

Note: Inpatient studies are required by Hospital Policy to utilize [Investigational Drug Service \(IDS\) pharmacies \(Oncology or Non-Oncology\)](#). Use of IDS is highly recommended, but optional for outpatient studies. Outpatient studies not using IDS services are subject to periodic inspection by the IDS for compliance with drug accountability good clinical practices.

Indicate where study drug(s) will be housed and managed:

 Investigational Drug Service (IDS) UK Hospital

Other Location:

Marijuana will be stored at the Robert Straus Research Facility in our secure Schedule I drug storage area. Alcohol will be stored at the IDS.

Is the study being conducted under a valid Investigational New Drug (IND) application?

 Yes No

If Yes, list IND #(s) and complete the following:

141123

IND Submitted/Held by:

Sponsor: Held By: Investigator: Held By: [name],
Ph.D.Other: Held By:

Checkmark if the study is being conducted under FDA's Expanded Access Program (e.g., Treatment IND) or if this is an Individual Patient Expanded Access IND ([FDA Form 3926](#)).

[FDA's Expanded Access Program Information for Individual Patient Expanded Access INDs](#), and attach the following:

- [FDA Form 3926](#);
- FDA expanded access approval or correspondence;
- Confirmation of agreement from manufacturer or entity authorized to provide access to the product.

For guidance and reporting requirements at the conclusion of treatment see the [Expanded Access SOP](#).

Complete and attach the required [Study Drug Form](#) picking "Study Drug Form" for the document type. Any applicable drug documentation (e.g., Investigator Brochure; approved labeling; publication; FDA correspondence, etc.) should be attached using "Other Drug Documentation" for the document type.

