The primary aim of this project is to enroll healthy occasional marijuana smokers as outpatients to examine the effects of vaporized marijuana strains containing 1) high concentrations of THC (30 mg THC), 2) moderate concentrations of THC + CBD (15 mg THC + 7.5 mg CBD), and 3) moderate concentration of THC (15 mg THC), in comparison to placebo marijuana (negative control) and an alcohol dose known to produce driving impairment (positive control), on simulated driving performance. Secondary aims include examining the abuse liability, cognitive/psychomotor performance, and physiological effects of the dose conditions; sex differences will also be explored.

Study Design

Describe and explain the study design (e.g., observational, secondary analysis, single/double blind, parallel, crossover, deception, etc.).

- *Clinical Research:* Indicate whether subjects will be randomized and whether subjects will receive any placebo.

- **Community-Based Participatory Research:** If you are conducting [community-based participatory research \(CBPR\)](#), describe strategies for involvement of community members in the design and implementation of the study, and dissemination of results from the study.
- **Qualitative research:** Indicate ranges where flexibility is needed, if a fixed interview transcript is not available, describe interview topics including the most sensitive potential questions.
- **Research Repositories:** If the purpose of this submission is to establish a Research Repository (bank, registry) and the material you plan to collect is already available from a commercial supplier, clinical lab, or established IRB approved research repository, provide scientific justification for establishing an additional repository collecting duplicate material. Describe the repository design and operating procedures. For relevant information to include, see the [UK Research Biospecimen Bank Guidance](#) or the [UK Research Registry Guidance](#).

This outpatient study will be conducted at the Straus Behavioral Science Research Facility and will last approximately 2-4 weeks per participant. This study will employ a within subject, randomized, double-blind, double-dummy, placebo-controlled crossover design to examine acute marijuana effects on driving performance and a variety of subjective and observer-rated measures.

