All volunteers receive medical and psychiatric screening and examination prior to study participation, including: 1) history and physical examination by a physician, 2) Beck Depression Inventory (screens for depression), 3) Symptom Checklist-90 (general psychiatric symptom inventory), 4) electrocardiogram, 5) laboratory testing (complete blood count with differential, complete metabolic panel, urinalysis with microscopic evaluation, urine drug testing, and urine pregnancy test for females), 6) literacy assessment and 7) evaluation of drug and alcohol use histories. Only those in good medical and psychiatric health, as determined by the study physician, are allowed to participate. Once a person meets inclusion/exclusion criteria, they will be permitted to begin participation in experimental study sessions.

General Methods: Participants will complete one to three training sessions to familiarize them to the driving simulator, the vaporizer procedure (using placebo marijuana), and the various computer tasks to insure that they are comfortable with the equipment and tasks prior to data collection. To familiarize participants with the smoking procedure, placebo marijuana will be administered; participants will be told that the vaporized dose is placebo. After this training is complete, the experimental sessions will be initiated.

Participants will complete a total of 5 experimental sessions. During each session, a battery of assessments will be conducted prior to (as a baseline evaluation) and at regular intervals 8 hours post marijuana dose. These assessments will include an array of subjective, cognitive and psychomotor tasks, driving simulator performance tasks and physiological assessments. The presentation of these assessments is based on the time-active curves for the drugs being tested. On session days, participants will arrive at the laboratory at approximately 9:00 am and will be scheduled to discharge at approximately 6:00 pm (total participation time will be approximately 9 hours).

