The content and flow of experimental sessions are designed to capture the time-action curves for the test agents at the selected doses (peak subjective effects of high potency marijuana ~ 15 mins – 3 hrs (Haney et al., 2016; Hunault et al., 2014; Ramaekers et al., 2006) alcohol (0.8 g/kg) ~ 15 min – 3 hrs (Kirkpatrick & de Wit, 2013)). The oral alcohol solution will be administered 15 minutes prior to smoked marijuana; however, only one agent will be active (i.e., active alcohol + placebo marijuana; active marijuana + placebo drink). Participants will vaporize marijuana (approx. 166 mg total weight). Driving simulation will be tested at six time points during each test session at baseline, 15 min and 1, 2, 4, and 6 hr post-marijuana dose. This will allow us to examine the driving ability 1) immediately after smoking (15 min), 2) during peak subjective ratings of feeling high (15 mins-2 hrs), (Hunault et al., 2014; Ramaekers et al., 2006) and 3) after subjective intoxication has subsided, but while sedation is expected to remain elevated (6 hrs). (Hunault et al., 2014)

Participants are required 1) to successfully complete a field sobriety test, 2) have a BAC = 0.02, and 3) report no acute intoxication in order to be discharged from the session. Free round-trip transportation will be provided for subject safety (e.g., taxi). Participants are not permitted to transport themselves home.

Study Drug

All drug doses will be stored at the UK Robert Straus Research Facility under secure conditions specially equipped for Schedule I drug storage. Doses will be blinded by the University of Kentucky (UK) Investigational Pharmacy licensed pharmacists (Drs. [name], [name]). Marijuana will be obtained through the NIDA drug supply. Each vaporized dose will contain approximately 166 mg of plant material. Research Triangle Institute (RTI) will provide chemical analysis reports of marijuana cannabinoid concentrations with each lot of marijuana, which will be reviewed by the PI for consistency. A Volcano brand vaporizer will be used to deliver the doses. This model has been used in several studies (e.g., Spindle et al., 2018; JAMA) and is more efficient delivery system than a marijuana cigarette (drug is lost through combustion and side stream smoke; a vaporizer is a closed system that eliminates these

concerns). Alcohol doses (USP-grade ethanol, juice mixer) and placebo drinks (juice with 1% alcohol) will be prepared by the pharmacists.

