Randomized orders will be generated by the statistician. All dosing will be double-blind; however, sealed dose orders will be available on-site and at the pharmacy in the event of an emergency. The drug formulation plans for these studies will be reviewed by the FDA before study initiation. The IND will be submitted after we obtain IRB approval.

Dose Selection

The doses of vaporized marijuana were selected as representative recreational and medicinal marijuana strains that are currently legally available in dispensaries across the U.S. (360, 2017; Sevigny, Pacula, & Heaton, 2014). Strains with 1) high THC/trace CBD, 2) high THC/moderate amounts of CBD are used for medicinal and recreational use (2:1 ratio), and 3) moderate amounts of THC alone (trace CBD) are all used for both medical and recreational purposes. (Lankenau et al., 2016; MA, 2014; Ko, Bober, Mindra, & Moreau, 2016; Kolikonda et al., 2016; Maa & Figi, 2014; 360, 2017; Belendiuk, Babson, Vandrey, & Bonn-Miller, 2015; Freeman & Winstock, 2015; Sevigny et al., 2014).

These doses will provide information regarding the effects of 1) a high dose of THC alone (approximately 30 mg vaporized THC), 2) a moderate dose of THC with CBD (approximately 15 mg THC + 7.5 mg CBD), and 3) moderate dose of THC (approximately 15 mg THC) allowing assessment of a two-fold dose range of THC compared to placebo marijuana (0 mg THC, 0 mg CBD) and will provide some information about the effects of THC combined with CBD. Comparator conditions of doses of CBD alone, or assessments of THC/CBD interactions will not be included in this small-scale exploratory study. The risk of lung infection from vaporized marijuana is stated in the consent form.

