We have developed driving scenario courses with comparable variables and construct characteristics for use in repeated testing designs. These driving scenarios are approximately 10 minutes in length and include various highway and city driving courses. We are familiar with the consensus recommendations from the International Council on Alcohol, Drugs & Traffic Safety's (ICADTS) for behavioral outcomes in drugged driving studies and will focus on those outcomes most commonly evaluated in driving simulator studies, for example, lateral position variability (i.e., a marker of lane deviation and tactical measures (deceleration maneuvering in response to an obstacle or yellow light). However, other variables will be explored.

Data will be collected for approximately 8 hours post-dose (e.g., relative to marijuana administration) and we expect total session participation time will be approximately 9 hours. A field sobriety test will be completed in the presence of an investigator or senior staff member before participants will be released to go home. If the participant exhibits signs of impairment, they will be retained at the laboratory and re-assessed every 20 minutes (and paid a rate of \$10/hr for this extra time). In our experience, the effects of marijuana are minimal at 8 hours post-dose and breath alcohol levels should be 0.00 – 0.02 at this time. Participants will not be permitted to transport themselves home under any circumstance. We will provide transportation (for example: taxi, Uber, similar car service). Alternatively, a participant can arrange for a friend/family member to provide transportation if they choose. We will also advise participants not to use drugs or alcohol on the day of session (either prior to or after the session has been completed) and not to drive a car or operate machinery for the remainder of the day. We have successfully administered smoked marijuana and alcohol on an outpatient basis using similar methods (Protocols #15-0976-F3R, #14-0769-F3R, #11-0100-F6A).

Sessions in which active drug doses are administered will be followed by at least one wash-out day prior to the next session (e.g., minimum of 48 hours between doses).

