Participants will be paid for each screening visit at the rate of \$50 per visit. If only a urinalysis or ECG or vital signs are needed subjects will be paid \$15. Volunteers will earn \$50 for each training session (approximately 4 hours in length) and \$25 for a 2- to 4-week follow-up appointment. Volunteers will earn \$80 base pay for each session in which they participate. They will also be paid \$5 per drive if the course is completed within the specified time limit (e.g., approx. 9 minutes). We anticipate completing 6 driving scenarios per session, so participants have the opportunity to earn up to an additional \$30/session. This money will be given to participants along with their base pay. Participants will be paid a study bonus of \$80/session if they complete each of the 5 sessions. If the volunteer chooses to leave before completing the study, they will not receive the completion bonus. However, if the participant is discharged early due to unrelated medical issues or investigator decision related to safety (e.g., an adverse reaction to the study drug), they will be paid the completion bonus for the duration of their participation. If participants complete all of the 6 sessions, they will receive a total payment of \$800 (not including screening, practice sessions, bonus pay for drive completion times, or follow-up payments).

Costs to Subjects

Include a list of services and/or tests that will not be paid for by the sponsor and/or the study (e.g., MRI, HIV). Keep in mind that a subject will not know what is "standard" – and thus not covered by the sponsor/study – unless you tell them.

There are no costs to volunteers who participate in this study.

Data and Safety Monitoring

The IRB requires review and approval of data and safety monitoring plans for greater than minimal risk research or NIH-funded/FDA-regulated clinical investigations.

- If you are conducting greater than minimal risk research, or your clinical investigation is NIH-funded, describe your Data and Safety Monitoring Plan (DSMP). [Click here for additional guidance on developing a Data and Safety Monitoring Plan](#).
- If this is a non-sponsored investigator-initiated protocol considered greater than minimal risk research, and if you are planning on using a Data and Safety Monitoring Board (DSMB) as part of your DSMP, [click here for additional guidance](#) for information to include with your IRB application.

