Study Title: Marijuana Effects on Simulated Driving Performance

Institution/Site:	University of Kentucky
Document (Approval/Update) Date:	IRB 12/26/23
NCT Number:	NCT03699540
IRB Number	43636
Coversheet created:	4/29/24

Statistical Analysis Plan

All analyses will be conducted using SAS Version 9.3 or higher (SAS Institute, Inc; Cary, NC, USA), and all hypothesis testing will be two-sided with a significance level of 0.05. P-values will be presented with 3 decimals and p-values that are less than 0.001 will be represented as <0.001.

Continuous data will be summarized using descriptive statistics: number of observations (n), arithmetic mean, standard error, minimum, and maximum. Frequencies and percentages will be used to summarize categorical (discrete) outcomes. Means and standard errors will be presented to two decimal places.

Demographics and Other Baseline Characteristics

Demographic and baseline characteristics will be summarized; no statistical comparisons will be made on demographic or baseline characteristics. The demographic and baseline characteristics will consist of age, sex, race, ethnicity, height (cm), weight (kg), and BMI (kg/m²).

Continuous variables (age, height, weight, BMI) will be summarized by n, mean, standard deviation, min, median, and max. Frequencies and percentages will be used to describe categorical (discrete) variables including gender, race, and ethnicity.

Analysis of Primary Outcomes

The primary Emax for Standard Deviation in Lane Position (SDLP: amount of weaving/swerving of the car in and out of the lane) and will be analyzed in a mixed model including the nine drug conditions with a compound symmetry covariance structure. Within each model, subject will be treated as random effects, and the remaining parameter as fixed effects. Mixed models are suited for data with repeated measures, correlations among observations within an individual subject, and the presence of missing data. The response of individual subjects is first modeled, and then the estimates for each individual are combined in a group analysis (Singer, 1998; Ballinger 2004; Diggle et al. 1996; Gibbons et al. 1993; Kreft and De Leeuw 1998). Tukey post-hoc tests will compare active doses to placebo and other relevant active dose comparisons.

Analysis of Secondary Outcomes

Secondary outcomes will include:

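### The crossover models have no session-number (period) effect and the order scheme is unstated; if SDLP drifts over the five sessions this costs precision but causes no systematic bias

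*Protocol*

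**What the plan says.** The protocol (Study Design) describes a "within subject, randomized, double-blind, double-dummy, placebo-controlled crossover design". Research Procedures, General Methods, states "Participants will complete a total of 5 experimental sessions" and also "Participants will complete one to three training sessions to familiarize them to the driving simulator", before data collection starts. The same section adds "Driving simulation will be tested at six time points during each test session", and the Payment section agrees: "We anticipate completing 6 driving scenarios per session".

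On order of dosing, the Study Drug text says "Randomized orders will be generated by the statistician" and nothing more. It names no Latin square, Williams set, blocking or sequence list, and it does not say that orders are unbalanced either. Outpatient Methods describes "driving scenario courses with comparable variables and construct characteristics for use in repeated testing designs".

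The SAP (Analysis of Primary Outcomes) analyses SDLP Emax in a mixed model on drug condition with compound symmetry, where "subject will be treated as random effects, and the remaining parameter as fixed effects". Analysis of Secondary Outcomes adds time within session where appropriate. The protocol's Data and Safety Monitoring section names a linear mixed model without listing its terms. No period, sequence or carryover term appears in either document, and the SAP does not say that Emax is adjusted for the pre-dose drive.

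**The concern.** SDLP is a measure of skill taken repeatedly on a simulator, so it may drift from session 1 to session 5. Participants arrive with one to three training sessions behind them, so prior exposure differs between people. They are also paid for finishing each drive within a time limit, which could change driving style with experience. A crossover model normally carries a period effect for this reason. Without one, any session trend stays in the error term of every condition contrast, including alcohol against placebo. If orders are simple random, two conditions can also sit at different average session positions by chance in the single list used. What is at stake is the precision of the comparisons and how well the reported standard errors reflect it.

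**Working it through.** The documents give no SD, effect size, power or practice effect, so there is no stated figure to reproduce.

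**Inputs.** N = 24 completers (Study Population), five conditions and five sessions (Objectives, General Methods), complete data, one SDLP Emax per session. Assumed: a linear session trend of b within-subject SD per session, with b = 0, 0.1, 0.2, 0.3. Over the study this is 4b = 0, 0.4, 0.8, 1.2 SD.

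**1. Chance imbalance under simple random orders.** A session position drawn uniformly from 1 to 5 has variance (25 - 1)/12 = 2. Two conditions in the same participant have covariance -2/4 = -0.5. Hence Var(difference in position) = 2 + 2 + 2(0.5) = 5 per participant, and the SD of the mean difference is sqrt(5/24) = 0.46 session. In simulated lists about 95% of pairs lie within 0.9 session. The largest gap among the five conditions has median 0.75 and 95th percentile 1.25. A 5x5 Latin square used as evenly as 24 allows brings the largest gap down to 0.17.

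**2. Cost of omitting the term, simple random orders.** With the within-subject SD set to 1, the contrast variance is 2/N + 5b²/N = (2/N)(1 + 2.5b²), so the SE factor is sqrt(1 + 2.5b²).

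**3. Cost of omitting the term, balanced orders.** The trend now cancels from the contrast itself, but its sum of squares, 10Nb², falls into a residual with 5N - N - 4 = 4N - 4 df. The residual variance becomes 1 + 2.5b²·N/(N - 1), about 1 + 2.6b². The reported SE is then too large by factors of about 1.01, 1.05 and 1.11 for b = 0.1, 0.2, 0.3. A balanced list therefore does not make the term unnecessary.

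**4. Cost of including the term.** Error df fall from 24×5 - 24 - 4 = 92 to 88. Under simple random orders, session and condition are also not orthogonal: the contrast SE goes from 0.289 to 0.295 within-subject SD, about 2.3%.

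**5. Net effect, simple random orders.**

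| b (SD per session) | SE factor if omitted | SE factor if included | Net gain from including |
|---|---|---|---|
| 0 | 1.000 | 1.023 | about -2% |
| 0.1 | 1.012 | 1.023 | about -1% |
| 0.2 | 1.049 | 1.023 | about +2.5% |
| 0.3 | 1.107 | 1.023 | about +8% |

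Break-even is where 2.5b² = 1.023² - 1 = 0.0465, so b is about 0.14 per session, or about 0.55 SD over the study.

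**6. Simulation check** (4,000 trials per setting, N = 24, simple random orders, an effect of 0.82 SD set to give about 80% power for one unadjusted pair with no trend). For a total trend of 0, 0.5, 1, 1.5 and 2 SD, power without the term is about 0.80, 0.79, 0.74, 0.68 and 0.60. With the term it stays at about 0.77 to 0.79. In both models the mean shift is about 0 and type I error is close to 0.05.

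**The case against.** The strongest reply has four parts.

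- **Randomised order already protects the comparisons.** This stands. A reader might infer that practice is confounded with drug condition, or that the false-positive rate is inflated. The documents do not support that: averaged over order lists there is no bias, type I error stays near 0.05, and chance imbalance is already reflected in the wider standard error. One particular list can still be unlucky. For a pair 0.9 session apart, the false-positive rate given that list is about 0.06 to 0.17 for total trends of 0.5 to 2 SD. That describes one realised list, not the procedure.
- **Silence on balance is not absence of balance.** This also stands. The protocol's wording fits a randomised Latin square as well as independent permutations, so the 0.46-session figure is conditional on the latter. By step 3, however, a balanced list still needs the term for its standard errors to be right.
- **The trend may be small.** Nothing in the documents shows that SDLP improves over sessions. Training sessions last about four hours each and the courses were built for repeated use, so a plateau is possible; if so, the term costs about 2%. The total of 5 × 6 = 30 test drives also overstates the exposure. Every session has the same six drives, so within-session practice is common to all conditions and only drift between sessions matters. The pre-dose drive could absorb such drift, but the SAP does not say it is used.
- **The study presents itself as small and exploratory.** That bears on priority, but not on whether the model should follow the design.

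**Conclusion.** The point holds as a gap in specification and precision. No session-number term appears in any planned model, and the order scheme is not stated. The consequence is added residual variance, plus chance imbalance if orders are simple random, or overstated standard errors if they are balanced. The loss from omission is 0% to 11% in SE over slopes of 0 to 0.3 SD per session. Under simple random orders the term pays for itself above about 0.14 SD per session. These slopes are assumptions.

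The figures also rest on five conditions and five sessions. The SAP refers to nine drug conditions, and the Payment section once speaks of six sessions, although its $800 total equals 5 × ($80 + $80). These statements must be reconciled before the error df can be fixed.

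**What to change.** Add session number (categorical, 1 to 5) as a fixed effect in the primary SDLP Emax model and in the secondary mixed models. If results have already been seen, report this as a sensitivity analysis labelled as such. The cost is 4 df and, under simple random orders, about 2.3% in SE when there is no trend. No new data are needed, because session number follows from the visit records.

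State in the protocol or SAP how the order list was generated. If orders remain to be assigned, draw them from a Latin-square or Williams-type list used as evenly as the number of completers allows. Exact balance is not possible at 24, which is a multiple of neither 5 nor 10, but near-balance is. If enrolment is complete, the model term alone is enough.

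Reconcile the number of conditions and sessions across the protocol and the SAP.
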